### 2.1. Principal research questions

1. Does combination therapy with quetiapine plus lamotrigine (Groups 1 & 2) lead to greater improvement in depressive symptoms over 12 weeks than quetiapine monotherapy plus lamotrigine placebo (Groups 3 & 4) in patients with bipolar depressive disorder?
2. Does adjunctive treatment with folic acid (Groups 1 & 3) lead to greater reduction in depressive symptoms by 12 weeks than folic acid placebo (Groups 2 & 4) in patients with bipolar depressive disorder?

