**3.2.3. Randomisation:** A randomisation visit should take place between 7 and 14 days after trial entry. If the dose of quetiapine has not been established within 14 days or an appointment cannot be made, the investigator should contact the CEQUEL office to request an extension. The randomisation visit will include checks that the participant is willing to enter the randomised phase and meets the eligibility criteria including uncertainty about optimum treatment.

A centralised randomisation service will be used. Investigators with internet access in their clinic room will access the service via the web. Investigators without internet

---

 If randomisation to folic acid/placebo is not feasible or appropriate, randomisation will be to lamotrigine/placebo only.

access will fax a randomisation form (together with a trial prescription form) to the CEQUEL Office. A member of the CEQUEL team will then perform the randomisation using the centralised system. Each participant will be randomised to either lamotrigine or lamotrigine placebo and also to either folic acid or folic acid placebo.

A non-deterministic minimisation algorithm will be used to produce treatment groups balanced for important prognostic factors. Trial sites will be arranged into geographical regions. The first 60 patients will be allocated randomly without minimisation to avoid predictability. Subsequently, the minimisation algorithm will be applied with an allocation ratio that is not fully deterministic: there will be an 80% bias in favour of allocations that minimise the imbalance.

The randomisation algorithm will minimise for 16 variables related to prognosis at baseline:

- bipolar I or bipolar II (based on DSM-IV criteria)
- baseline severity of depression (QIDS-SR16) – 4 categories: mild ≤10, moderate 11-15, severe 16-20 and very severe ≥ 21
- age – classified as ≤ 30, 31-40, 41-50 and > 50
- gender
- dose of quetiapine (150mg/day; >150 to < 300mg; 300mg/day; >300mg/day)
- concurrent medicines: the algorithm will minimise on each of 7 treatments - lithium, valproate, other mood stabiliser, olanzapine, other atypical antipsychotic, conventional antipsychotic and antidepressant
- pre-screening treatment with quetiapine
- pre- screening treatment with lamotrigine
- number of mood episodes in the past year (< 4 or ≥ 4)
- trial region

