Once randomisation has taken place the trial management program will generate a letter to the participant confirming that randomisation has taken place. The letter, prescription form and a list of pack numbers (see section 6.7.1.) will be sent to the trial pharmacy. At the pharmacy the appropriate packs of medicines will be dispensed and sent to the participant (or other agreed recipient) together with the letter. All participants will continue to be prescribed open-label quetiapine according to routine practice.

**3.2.4. Minimisation of Bias:** The centralised randomisation system guarantees complete allocation concealment and prevents subversion of randomisation.

Double-blind investigational treatments will minimise performance and ascertainment biases. Use of placebo to conceal treatments should be effective because neither lamotrigine nor folic acid cause easily recognisable adverse reaction and both are generally well-tolerated.

Multiple methods of minimising loss to follow-up, including telephone follow-up, will be employed to avoid attrition bias. The main statistical analysis will be carried out on the basis of intention-to-treat i.e. after randomisation, data for each participant will be analysed according to the treatment they were allocated irrespective of what treatment they actually received. This removes any elements of subjectivity in deciding whom to include in the analysis (and thus the risk of selection bias).

---

 If randomisation to folic acid/placebo is not feasible or appropriate, randomisation will be to lamotrigine/placebo only.

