###### 4.1.2. Exclusion criteria:

1. definite indications or contraindications to lamotrigine, quetiapine or folic acid\* (Including pregnancy and planned pregnancy)
2. new course of a specific psychosocial intervention started in the past 4 weeks
3. first appointment for a specific psychosocial intervention booked within the next 14 weeks
4. In the opinion of the investigator, currently experiencing manic or mixed episode.
5. primary diagnosis of schizophrenia

Plus, for women of child-bearing potential

6. currently breast feeding or not using adequate contraception.

\* Participants who have active cancer, a diagnosed pre-malignant condition, a strong family history of cancer or are unwilling to stop taking folic acid supplements can, where clinically appropriate, be randomised to the lamotrigine/placebo arm (see section 3.2.3.)

---

 Defined as Cognitive Behaviour Therapy (CBT), Group Psychoeducation, Family-focused Therapy and Interpersonal and Social Rhythm Therapy (IPSRT)

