### 9.2. Number of participants

The primary outcome is the level of depressive symptoms, measured using the QIDS-SR16. For comparisons of treatment groups at the margins as detailed in section 2.1, a minimum total sample size of 236 randomised participants (59 per arm) is required to detect a clinically important treatment effect on this outcome. This assumes a 20% loss to follow-up. Sample size has been calculated for the principal comparison for the primary outcome measure, the effect of lamotrigine on the primary outcome. A power of 90%, a 5% level of statistical significance, use of two-sided statistical tests throughout and an equal allocation to each arm have been assumed.

*9.2.1. Main effect of lamotrigine on primary outcome:* An absolute difference of 2 points on the QIDS score between Quetiapine+Placebo and Quetiapine+Lamotrigine is considered to be clinically important. From previous data, it has been estimated that the standard deviation of the QIDS in this population is 5.4. In order to detect this standardised difference of 0.37, a total of 186 randomised patients are required. This assumes a repeated measures analysis with 3 time points and a correlation between time points of 0.4. Allowing for a 20% loss to follow-up this increases to 236.

*9.2.2. Main effect of folic acid on primary outcome:* There is currently no QIDS-SR16 data available to assess the effect of folic acid. However, a total sample size of 186 gives the following power for a given effect size:

Effect size	Power
0.2	42%
0.25	60%
0.3	75%
0.35	87%

**9.2.3. Gene-treatment interaction (MTHFR C677T), (COMT Val158Met) and (FOLH1 T484C):** There are currently no QIDS-SR16 data available in the effect of treatment by genes. Therefore, we will conduct an exploratory analysis of the possible interactions between the genes MTHFR C677T, COMT Val158Met or FOLH1 T484C and response to treatment with folic acid.

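### Folic acid power is stated at 186, the full lamotrigine total, although some participants may be randomised to lamotrigine or its placebo only

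*Protocol*

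**What the plan says.** **The lamotrigine-only route.** The protocol's footnote to section 3.2 reads: "If randomisation to folic acid/placebo is not feasible or appropriate, randomisation will be to lamotrigine/placebo only". The note to section 4.1.2 names who may take this route. Besides people with active cancer or a diagnosed pre-malignant condition, it says that those with "a strong family history of cancer or are unwilling to stop taking folic acid supplements can, where clinically appropriate, be randomised to the lamotrigine/placebo arm". No limit or expected number is given. Section 6.5.2 asks for folic acid to be stopped except where there are reasons not to randomise to folate or placebo, so some of these participants may be taking folic acid.

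**The comparisons.** Section 2.1 labels both principal comparisons by four groups. For lamotrigine: "Does combination therapy with quetiapine plus lamotrigine (Groups 1 & 2) lead to greater improvement in depressive symptoms over 12 weeks", against Groups 3 and 4. For folic acid: "Does adjunctive treatment with folic acid (Groups 1 & 3) lead to greater reduction in depressive symptoms by 12 weeks", against folic acid placebo in Groups 2 and 4. Each of the four groups therefore carries either folic acid or its placebo.

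**The analysis.** Section 3.2.4 states the intention-to-treat rule: "data for each participant will be analysed according to the treatment they were allocated irrespective of what treatment they actually received". Section 9.1 applies intention-to-treat to the comparisons of section 2.1, analyses them at the margins, and adjusts the binary-outcome model for the other intervention.

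**The sample size.** Section 9.2 gives 236 randomised participants, 59 per arm, sized on the lamotrigine effect. Section 9.2.1 derives 186 before loss to follow-up. Section 9.2.2 applies the same 186 to folic acid: "However, a total sample size of 186 gives the following power for a given effect size". It lists power of 42, 60, 75 and 87% at effect sizes 0.2, 0.25, 0.3 and 0.35.

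**The concern.** Sections 9.2 and 9.2.2 treat every participant as entering both randomisations, while sections 3.2 and 4.1.2 say that some will enter only one. Folic acid is one of the two principal questions, and the power table is the only statement of what the trial can show on it. If part of the 186 has no folic acid allocation, the table describes a comparison larger than the permitted design delivers.

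A second, smaller difficulty follows. Lamotrigine-only participants belong to none of Groups 1 to 4, and a model that adjusts for the folic acid allocation has no value to give them. Unless the text says otherwise, an analyst could lose them through a missing covariate, or code them as folic acid placebo although they were never randomised to it and may be taking folic acid.

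**Working it through.** **Inputs, all from sections 9.2 to 9.2.2:** two-sided 5% level; 90% power; equal allocation; standardised difference 0.37 (2 points, SD 5.4); three time points with correlation 0.4; 20% loss to follow-up.

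**Step 1: reproduce the plan's own figures.**

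- Variance factor for the mean of three measures: (1 + 2 × 0.4)/3 = 0.6.
- Number per side: 2 × 0.6 × (1.960 + 1.282)² / 0.37² = 92.1, rounded up to 93, so 186 in total. This matches.
- Loss to follow-up: 186/0.8 = 232.5, which becomes 236 when rounded up to a multiple of four; 236/4 = 59. This matches.
- Folic acid power: Φ(ES × √(n/(2 × 0.6)) − 1.96), with n = 93 per side. At 0.30 this is Φ(0.30 × 8.803 − 1.96) = Φ(0.681) = 75.2%. Across the four effect sizes it gives 42.1, 59.5, 75.2 and 86.9%, against the stated 42, 60, 75 and 87%.

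So the table is right for 186, and it requires all 186 to be in the folic acid comparison.

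**Step 2: remove a lamotrigine-only share f.** The documents give no value of f, so the shares below are assumptions. Loss to follow-up is taken to be the same in both kinds of participant. Then n = 93 × (1 − f) per side.

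| Assumed share f | Folic acid total, 186 × (1 − f) | ES 0.20 | ES 0.25 | ES 0.30 | ES 0.35 |
|---|---|---|---|---|---|
| 0 (as stated) | 186 | 42% | 60% | 75% | 87% |
| 5% | about 177 | 40% | 57% | 73% | 85% |
| 10% | about 167 | 39% | 55% | 71% | 83% |
| 20% | about 149 | 35% | 50% | 66% | 79% |

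Depending on the effect size, the loss passes two percentage points at a share of about 4 to 6%.

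**Step 3: is there slack?** 236 × 0.8 = 188.8, about 3 more than 186. This covers a share of under 2%.

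**Step 4: the arm size.** With 236 randomised, the four factorial arms hold 236 × (1 − f)/4 each: about 56, 53 or 47 at shares of 5, 10 or 20%, not 59.

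**Step 5: who is in which comparison.** Sections 3.2.4 and 9.1 keep every allocated participant in the lamotrigine margin. Section 2.1 restricts the folic acid comparator to folic acid placebo. Together these imply that everyone is in the lamotrigine comparison and only those randomised to folic acid or its placebo are in the other. That reading is coherent, but sections 2.1, 9.1 and 9.2 do not state it, and the group labels and the adjustment for the other intervention do not accommodate it. The contents of Figure 3 and the Appendix 1 flow chart could not be read; the groups are taken from section 2.1 and the split into four arms of 59.

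**The case against.** The strongest defence has four parts.

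- **The table is arithmetically correct and conditional.** It says what a total of 186 gives. It is a grid without a target effect or power, the trial is sized on lamotrigine, and 236 is a minimum. All of this stands, and a reader who inferred a miscalculation would be wrong. What remains is that 186 is offered as the number available for folic acid, and the permitted design does not deliver it from 236 once the lamotrigine-only share exceeds about 2%.
- **Intention-to-treat is not breached.** A reader might infer from the group labels that randomised participants are dropped from the lamotrigine comparison. If they were, its power at 2/5.4 would fall from 90.3% to 88.8, 87.1 or 83.1% at shares of 5, 10 or 20%. But no section says they are dropped, and the intention-to-treat statements point the other way. The labels fit badly; they do not exclude anyone.
- **Randomisation to folic acid is not breached.** A reader might also infer that lamotrigine-only participants would be pooled with folic acid placebo. No section proposes this, and section 2.1 names folic acid placebo as the comparator. That the two margins have different populations is a normal consequence of partial randomisation, not an error.
- **Analysis sets and factor coding usually belong in the statistical analysis plan.** This is fair, and that plan is not at hand. It weakens the point about the adjustment. It does not touch the power table and the arm size, which the protocol itself fixes.

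**Conclusion.** The point holds as an inconsistency between the randomisation rules and the sample size section. The folic acid power figures are overstated to the extent that participants are randomised for lamotrigine only. The size rests entirely on an assumed share: about 2 percentage points at 5%, about 4 at 10%, and 8 to 10 at 20%, for effect sizes 0.30 and 0.35. Below about 5% the matter is minor; at 10 to 20% it is material for a principal question. These figures use the protocol's own variance factor of 0.6 and equal loss to follow-up.

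The mismatch with the Group 1 to 4 labels and with the adjustment for the other intervention is a gap in definition. It does not show that lamotrigine power is lost or that either randomisation is compromised. The correction is worth making because it is cheap and settles who counts in each comparison before the data are seen.

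**What to change.** - **Section 9.2.2:** replace 186 by the number expected to enter the folic acid randomisation and remain evaluable, and restate the power. If no expected share can be given, show power over a range of shares, as in the table above.
- **Section 9.2:** correct the 59 per arm, or state that it assumes everyone enters both randomisations.
- **Sections 2.1 and 9.1:** state that the lamotrigine comparison includes everyone randomised to lamotrigine or its placebo, and that the folic acid and gene-by-folic-acid analyses include only those randomised to folic acid or its placebo.
- **Adjustment in section 9.1:** where the lamotrigine model adjusts for folic acid, use a third level for participants not randomised to it, so that they are neither dropped nor coded as folic acid placebo. The statistical analysis plan may carry this detail if the protocol states the principle.

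The cost is a few sentences and one recalculated table. Recruitment and treatment do not change, and the stated folic acid power becomes slightly less favourable. The sample size need not rise, because it is set by lamotrigine. If 186 evaluable for folic acid were wanted, the total randomised would be 186/(0.8 × (1 − f)), or about 245, 259 or 291 at shares of 5, 10 or 20%.

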### **9.3. Criteria for the termination of the trial**

Prior to the start of recruitment, the dataset that will be required by the Independent Data Monitoring and Ethics Committee (IDMEC) (Chair - [name]) for interim analyses will be agreed. Stopping rules will also be agreed which specify the point at which interim results will be judged to be sufficiently conclusive for it to be appropriate for the IDMEC to recommend to the Trial Steering Committee (Chair - [name]) that they consider early termination of the trial.

### **10. Direct Access to Source Data/Documents**

The investigator(s)/institution(s) will permit trial-related monitoring, audits, REC review, and regulatory inspection(s), providing direct access to source data/documents to authorised auditors and monitors.

### **11. Quality Control and Quality Assurance Procedures**

Data will be evaluated for compliance with the protocol and accuracy in relation to source documents. The trial will be conducted in accordance with procedures identified in the protocol. Standard Operating Procedures (SOPs) will be used at all clinical and laboratory sites. Regular monitoring will be performed according to ICH-GCP. Following written SOPs, the monitors will verify that the clinical trial is conducted and data are generated, documented and reported in compliance with the protocol, GCP and the applicable regulatory requirements. When requested, the investigator site will provide direct access to all trial related source data/documents and reports for the purpose of monitoring and auditing by the sponsor, and inspection by local and regulatory authorities.

### **12. Ethics and Good Clinical Practice**

#### **12.1. Declaration of Helsinki**

The Investigator will ensure that the trial is conducted in full conformity with the current revision of the Declaration of Helsinki (last amended October 2000, with additional footnotes added 2002 and 2004).

### **12.2. ICH Guidelines for Good Clinical Practice**

The Investigator will ensure that the trial is conducted in full conformity with relevant regulations and with the ICH Guidelines for Good Clinical Practice (CPMP/ICH/135/95) July 1996.

### **12.3. Informed Consent**

Participant information sheets and consent forms will be provided so that patients can find out more about the trial before deciding whether or not to participate. The information will also be presented verbally by the investigator (or, at the investigator's request and with the patient's permission, by a member of the CEQUEL team). The information will include an explanation of the exact nature of the trial; the requirements of the protocol; any known adverse effects of trial medicines and any known risks involved in taking part. It will be clearly stated that the patient is free to withdraw from the trial at any time for any reason without prejudice to future care, and with no obligation to give the reason for withdrawal.

The patient will be allowed as much time as they want to consider the information, and the opportunity to question the investigator, their GP or other independent parties to decide whether to participate in the trial. Written Informed Consent will then be obtained by means of patient dated signature and signature of the Principal Investigator or named Co-Investigator. The informed consent will include permission for the CEQUEL office to notify the patient's GP about the trial and the allocated treatment. A copy of the signed Informed Consent will be given to the patient. The original signed form will be retained at the trial site.

### **12.4. Research Ethics Committee**

A copy of the protocol, proposed informed consent form, other written patient information and any proposed advertising material will be submitted to a REC for written approval.

The Investigator will submit and, where necessary, obtain approval from the REC for all subsequent protocol amendments and changes to the informed consent document.

### **12.5. Patient confidentiality**

The CEQUEL Office will need to be informed of participants' names and addresses in order to arrange for allocated treatments to be mailed to them. The Participant Information Sheet will inform patients of this and the number of staff with access to identifiable information will be kept to the minimum required to ensure smooth running of the trial.

Wherever possible forms containing clinical data will be contain only the participant's initials and a participant ID number assigned after entry to the run-in phase. All documents will be stored securely and kept in strict confidence in compliance with the Data Protection Act 1998

## **13. Data Handling and Record Keeping**

Electronic trial data will be stored on a secure database server with restricted access. All identifiable information will be encrypted in the database so that, in the unlikely event of a security breach, it would not be a straightforward matter to obtain participant details from the database. The database will be backed up daily in encrypted form and offsite copies will be made at regular intervals. Paper forms will be kept in a locked filing cabinet in the CEQUEL office. (The office is locked when empty.)

## **14. Financing and Insurance**

### **14.1. Funding**

CEQUEL is funded by the NIHR Efficacy and Mechanism Evaluation programme. The funding is held by the trial sponsor, the University of Oxford.

### **14.2. Non-negligent harm**

Indemnity and/or compensation for harm arising specifically from an accidental injury, and occurring as a consequence of the research participant's participation in the trial for which the University is the research sponsor will be covered by the University of Oxford.

### **14.3. Negligent Harm**

Indemnity and/or compensation for negligent harm arising specifically from an accidental injury for which the University is legally liable as the research sponsor will be covered by the University of Oxford. The NHS will owe a duty of care to those undergoing clinical treatment, with Trust Indemnity available through the NHS Litigation Authority Scheme.

## **15. Publication Policy**

The primary report will be submitted to a high impact medical journal and will be attributed to the CEQUEL Investigators and Collaborators. The names of all investigators who enter a participant into the randomised phase and of members of the trial management team will be listed at the end of the primary publication. The results will be further disseminated via systematic reviews, guidelines and evidence syntheses. Health economic analyses and results will be reported to field conferences and journals.

Protocol OCTUMI-02:CEQUEL version 06

Date: 15/05/2013

EUdraCT No.: 2007-004513-33

REC No. 08/H0605/39

CTA: 20584/0234/001-0001

ISRCTN17054996

**Appendix 1: Flow chart showing stages of the trial**

Protocol OCTUMI-02:CEQUEL version 06

Date: 15/05/2013

EUdraCT No.: 2007-004513-33

REC No. 08/H0605/39

CTA: 20584/0234/001-0001

ISRCTN17054996

**Appendix 2: Classification of adverse events**

A. Assessment of whether an adverse event is SERIOUS		
	YES	NO
1. Has the participant died?		
2. Was the participant at risk of death because of the AE?		
3. Did the AE lead to admission or extension of admission to hospital?		
4. Has the AE resulted in persistent or significant disability/incapacity?		
5. Was the AE an important medical event that may jeopardise the participant (or an unborn child) and may require medical or surgical intervention to prevent one of the outcomes listed above?		
⇒ If YES to ANY of the questions above, the event is SERIOUS ⇒		

B. Assessment of whether an event is a SUSPECTED ADVERSE REACTION		
	YES	NO
Is a causal relationship between a trial medicine and the adverse event at least a possibility? i.e. a relationship cannot be ruled out.		
⇒ If YES, the event should be classed as a SUSPECTED ADVERSE REACTION ⇒		

C. Assessment of EXPECTEDNESS (Suspected Serious Adverse Reactions only)		
	YES	NO
Is the nature of the adverse reaction consistent with the Summary of Product Characteristics or other relevant product information?		
⇒ If NO, the event should be classed as an UNEXPECTED REACTION ⇒

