### 8.1. Definitions

**8.1.1. Adverse Event (AE):** Any untoward medical occurrence in a trial participant administered a medicinal product, which does not necessarily have to have a causal relationship with this treatment (the trial medication).

An AE can therefore be any unfavourable and unintended sign (including an abnormal laboratory finding), symptom or disease temporally associated with the use of the trial medication, whether or not considered related to the trial medication.

**8.1.2. Adverse Reaction (AR):** All untoward and unintended responses to a medicinal product related to any dose. Response is taken to mean that a causal relationship between a trial medication and an AE is at least a reasonable possibility, i.e., the relationship cannot be ruled out.

**8.1.3. Serious or Severe Adverse Events:** To ensure no confusion or misunderstanding of the difference between the terms "serious" and "severe", which are not synonymous, the following note of clarification is provided:

The term "severe" is often used to describe the intensity (severity) of a specific event (as in mild, moderate, or severe myocardial infarction); the event itself, however, may be of relatively minor medical significance (such as severe headache). This is not the same as "serious," which is based on patient/event outcome or action criteria usually associated with events that pose a threat to a patient's life or functioning. Seriousness (not severity) serves as a guide for defining regulatory reporting obligations.

**8.1.4. Serious Adverse Event or Serious Adverse Reaction:** A serious adverse event or reaction is any untoward medical occurrence that at any dose:

- results in death
- is life-threatening (see note below)
- requires inpatient hospitalisation or prolongation of existing hospitalisation,
- results in persistent or significant disability/incapacity, or
- Is a congenital anomaly/birth defect.

**NOTE:** The term "life-threatening" in the definition of "serious" refers to an event in which the patient was at risk of death at the time of the event; it does not refer to an event which hypothetically might have caused death if it were more severe.

Medical and scientific judgment should be exercised in deciding whether an adverse event is serious in other situations.

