**8.1.5. Suspected Unexpected Serious Adverse Reactions (SUSARs):** A serious adverse reaction, the nature or severity of which is not consistent with the applicable product information (e.g., Investigator's Brochure for an unapproved investigational product or pack insert/summary of product characteristics for an approved product).

**8.1.6. Assessment of causality:** All cases judged by either the reporting medically qualified professional or the sponsor as having a reasonable suspected causal relationship to the trial medication qualify as adverse reactions.

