## **8.2. Serious Adverse Event Reporting Procedures**

**8.2.1. Reporting by investigator:** All SAEs, except those SARs that do not require immediate reporting (see 8.2.3.), must be reported to the Chief Investigator (CI) within one working day of discovery or notification of the event. All SAE information must be recorded on an SAE form and emailed/faxed to the CI. Additional information received for an event (follow-up or corrections to the original event data) need to be detailed on a new SAE form and sent/faxed to the sponsor.

In addition to SAE reporting, investigators should report to the CI any non-serious adverse reactions that they consider to be unexpected or for which they consider the severity or duration to be greater than that indicated in the Summary of Product Characteristics (SmPC). Adverse events that lead to withdrawal from the run-in phase or termination of any of the trial treatments during the randomised phase should also be reported.

Investigators are not required to report other non-serious adverse events.

**8.2.2. Reporting by the Chief Investigator:** The CI will:

- report all SUSARs to the Competent Authorities (MHRA in the UK) and the REC concerned. Fatal or life-threatening SUSARs must be reported within 7 days and all other SUSARs within 15 days
- report all SAEs (including SUSARs) to the participant's NHS Trust and to the IDMEC
- inform all investigators concerned of relevant information about SUSARs that could adversely affect the safety of participants.

In addition to the expedited reporting above, the CI will:

- submit once a year throughout the clinical trial or on request a safety report to the Competent Authority (MHRA in the UK), the main REC and participating NHS Trusts and send a copy to the University of Oxford Clinical Trials Research Governance Team.
- provide data on all reported AEs to the IDMEC as required.

**8.2.3. Expected Serious Adverse Reactions:** Immediate reporting of Suspected Serious Adverse Reactions that are listed in the SmPC for the appropriate trial treatment(s) will not be required provided that the severity and seriousness are consistent with the information given in the SmPC.

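### Appendix 2 tests expectedness by nature alone and has no birth-defect item, so the classification form does not match the definitions in Section 8.1

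*Protocol*

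**What the plan says.** Section 8 of the protocol opens by pointing the reader to Appendix 2, a three-part form for classifying adverse events.

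**Expectedness.** Section 8.1.5 defines a SUSAR as a serious adverse reaction "the nature or severity of which is not consistent with the applicable product information". Section 8.2.3 excuses a reaction listed in the SmPC from immediate reporting, but only "provided that the severity and seriousness are consistent with the information given in the SmPC". Part C of the form, completed for suspected serious reactions only, asks "Is the nature of the adverse reaction consistent with the Summary of Product Characteristics or other relevant product information" and classes the reaction as unexpected if the answer is no.

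**Seriousness.** Section 8.1.4 gives five criteria. The last reads "Is a congenital anomaly/birth defect". It then adds: "Medical and scientific judgment should be exercised in deciding whether an adverse event is serious in other situations". Part A of the form has five yes/no items. Item 4 asks "Has the AE resulted in persistent or significant disability/incapacity". Item 5 asks "Was the AE an important medical event that may jeopardise the participant (or an unborn child) and may require medical or surgical intervention", where the intervention is meant to avert an outcome named in the items before it. The rule beneath is "If YES to ANY of the questions above, the event is SERIOUS". No item names a birth defect.

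**The concern.** Two places in one protocol classify the same event, and for some events they disagree. Expectedness separates a SUSAR from other serious reactions. Under 8.2.2 a SUSAR must go to the competent authority and the ethics committee within 7 days if fatal or life-threatening, and within 15 days otherwise. A form that leaves severity out invites a more-severe-than-labelled reaction to be filed as expected.

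Severity is not incidental in this protocol. Section 8.2.1 asks investigators to report even non-serious reactions whose severity or duration exceeds the SmPC. Section 1.3.2 describes skin reactions to lamotrigine that run from rash in up to 10% of patients to rare, severe forms. The SmPC is not part of the document, so this shows only that degree matters here, not how any particular reaction would be classed.

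**Working it through.** No arithmetic applies beyond one interval. The check sets the definitions beside the form.

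**Step 1: expectedness.** Inputs are the two-part test in 8.1.5 (nature or severity) and the single test in Part C (nature). There are four possible combinations for a serious suspected reaction:

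| Nature fits product information | Severity fits | 8.1.5 | Part C answer | Agreement |
|---|---|---|---|---|
| Yes | Yes | Not unexpected | Yes | Agree |
| No | Yes | Unexpected | No, so unexpected | Agree |
| No | No | Unexpected | No, so unexpected | Agree |
| Yes | No | Unexpected (SUSAR) | Yes, so not marked unexpected | **Disagree** |

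The form differs from the definition in one of the four cases, and only towards under-classification.

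**Step 2: seriousness.** Inputs are the criteria of 8.1.4 and the items of Part A:

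| 8.1.4 | Part A |
|---|---|
| Death | Item 1 |
| Life-threatening | Item 2 |
| Admission or prolonged admission | Item 3 |
| Disability or incapacity | Item 4 |
| Congenital anomaly or birth defect | **No item** |
| Other situations, by judgement | Item 5 (important medical event) |

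Item 5 mentions an unborn child, but ties the intervention to preventing an outcome already listed, and birth defect is not listed. A birth defect with no death, risk of death, admission, lasting disability or preventive intervention therefore gets five negative answers in Part A, although 8.1.4 makes it serious. A birth defect that meets any of those conditions is caught.

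**Step 3: where a misclassified reaction would go.** By 8.2.1, a serious event that 8.2.3 does not exempt must reach the Chief Investigator within one working day. If a site scored the reaction as expected on the form and on that basis alone did not report it at once, the event would still have to be entered in the CRF under 8.3, which sets no deadline. The scheduled investigator forms that collect serious events fall at 12, 22 and 52 weeks (Sections 5.3 to 5.5), so the longest nominal interval is 52 − 22 = 30 weeks. Other routes could bring the event to light sooner: reports of events that end trial treatment (8.2.1) and participants' monthly reports of contact with services (5.6). Neither asks whether severity exceeds the product information.

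**The case against.** The strongest reply is that the operative rules already state the severity test, and most of that reply stands.

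- A reader might infer that a listed but more severe reaction escapes immediate reporting under 8.2.3. The text does not support this. The waiver depends on consistent severity and seriousness and does not refer to Part C. Such a reaction fails the condition and stays under the one-working-day rule.
- The Chief Investigator is responsible for SUSAR reports under 8.2.2 and has the definition in 8.1.5 to work from. Severity and relatedness are recorded for every serious event (8.3), and all serious events go to the IDMEC (8.2.2).
- Nothing says that the form overrides Section 8, or who completes it. Strictly, Part C states only what follows from a no, and Part A only what follows from a yes. Neither states the converse, and 8.1.4 keeps room for judgement.
- A reader might also infer that every birth defect would be missed. That goes too far: items 4 and 5 catch some, pregnancy and inadequate contraception are exclusions (4.1.2), and 8.3 requires any pregnancy and its outcome to be reported to the Chief Investigator.
- Nor is the form narrower throughout. By naming important medical events it is more explicit than 8.1.4, and that difference cannot cause under-reporting.

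What the reply does not remove is the mismatch itself. A yes/no checklist is normally read in both directions, Section 8 sends its reader to this one, and for the case found in Step 1 it points away from the protocol's own definition. The pregnancy rule in 8.3 sets no deadline and does not class the outcome as serious.

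**Conclusion.** The point holds as an internal inconsistency in safety classification. The main defect is Part C: followed on its own, it leaves a listed but more severe serious reaction unmarked where 8.1.5 calls it unexpected. The missing birth-defect item in Part A is a real but lesser defect, with partial safeguards elsewhere.

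The practical risk rests on one assumption: that someone classifies from the form without returning to 8.1 and 8.2. The protocol neither requires nor rules out that practice. The number of events cannot be estimated, because the protocol gives no expected rate of serious reactions or of pregnancies. With 236 participants planned it is likely to be small. Sample size, power and efficacy analyses are unaffected. The correction is worth making because it concerns participant safety and costs almost nothing.

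**What to change.** 1. In Appendix 2 Part C, ask whether both the nature and the severity of the reaction are consistent with the product information, with a no on either making it unexpected. This brings the form into line with 8.1.5 and with the severity condition in 8.2.3.
2. In Appendix 2 Part A, add an item for congenital anomaly or birth defect, as in 8.1.4.

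Naming important medical events in 8.1.4 would make the two lists identical. It is optional and not part of the error.

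The cost is two lines on a form and the matching update to any site copies. Both changes adopt definitions already in the protocol. No clinical rule, data item for analysis or statistical method changes. Serious reactions already classified with the form could be checked once against 8.1.4 and 8.1.5.
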